- Naloxone (opioid antidote) was administered approximately once a day in Seattle by medics attending to opioid overdoses in 2011. Almost all are transported to the HMC ED.
- On August 22, 2012 the Director of the Office of National Drug Control Policy, Gil Kerlikowske, called for increased action to prevent drug overdose deaths, including wider distribution of naloxone.

Objectives

Primary Aims

The primary aims are to test whether those who receive the intervention compared to standard care have:

[figure not shown]
- 1) Lower rates of opioid non-fatal and fatal overdose
- 2) Reduce drug use, in appropriate medication use, and other overdose risk behaviors

Secondary Aims

The secondary aims are to test whether those who receive the intervention compared to standard care have:

- 3) More appropriate health care utilization (e.g. fewer emergency department visits and admissions to inpatient care)
- 4) Lower total health care costs
- 5) Determine the prevalence of HIV risk behaviors among heroin and pharmaceutical opioid users at risk for overdose and whether the intervention impacts these behaviors.

Study Design

This prospective, multi-site, randomized clinical trial will compare standard care to a novel intervention that combines OOPEN with BBCC for heroin users (n=500) and pharmaceutical opioid users at elevated risk for overdose (n=500). The study will take place at Harborview Medical Center (HMC) , University of Washington Medical Center (UWMC), and Evergreen Treatment Services. The primary outcomes are subsequent opioid overdoses, ascertained by self-report interviews at 3, 6 and 12 months after recruitment as well as via administrative records for at least 24 months and self-reported drug use and other overdose risk behaviors. Secondary outcomes include: health care utilization, direct health care costs and impact on HIV risk behaviors.

Eligibility Criteria

Inclusion for all subjects:

- 1) Meets study definition of elevated risk of future opioid overdose
 - Reason for visit is opioid overdose (regardless of frequency of use), or
 - Use of pharmaceutical opioids not prescribed to the patient 2 or more times in the prior month, or
 - Use of other opioids, alcohol, benzodiazepines or stimulants within two hours of using opioids 2 or more times in the prior month, or
 - Average daily dose of prescribed opioids consumed is greater than 10 mg morphine equivalent analgesic dose or higher for 15 or more days in the last 30.

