- 2) Overdose Risk Assessment: This assessment is used to determine the potential for future overdose based on prior overdose history, current drug use practices and social context for current drug use. This assessment is not standardized but is compiled from individual items of known risk factors for overdose.
- 3) World Health Organization Quality of Life (WHOQOL-BREF). This is a short assessment to measure general health and physical, social and emotional functioning.
- 4) World Health Organization Alcohol, Smoking and Substance Involvement Screening Test (WHO-ASSIST v.3). This is a multi-item tool to determine areas of substance use and misuse. This assessment battery screens for recent and lifetime use of a variety of substances, including illicit drugs, alcohol, pharmaceuticals and tobacco products.
- 5) Age of First Use: Subjects are asked to provide the ages they first used a variety of substances.
- 6) HIV Risk Assessment Battery: This assessment is used to determine the potential for contracting HIV, hepatitis and other blood-borne illnesses based on drug use and sexual use behaviors.
- 7) Overdose History: This assessment will collect information related to any prior overdose that the subject has experienced or witnessed.
- 8) EQ-5D-3L: This validated quality of life measure asks about problems in mobility, self-care, usual activities, pain and discomfort, anxiety and depression and overall health.

Locator information:

Subjects will be asked to provide a number of sources to ensure they can be contacted for 3, 6 and 12 month follow-up visits. However, because we anticipate a number of high risk subjects to be indigent, subjects may be enrolled if they provide at least one primary source of locator information.

Randomization

Subjects will be randomized to receive either standard of care or the study intervention. We will recruit equal numbers of subjects in the intervention and control arms of the study, meeting eligibility criteria as heroin user or primarily pharmaceutical opioid users.

Follow-up Visits

Follow-up visits will occur at 3, 6 and 12-month after enrollment. All interviews will be by phone. Most assessments given at the baseline interview will be repeated at each follow-up

point. In addition to the assessments subjects will be asked questions about whether they have naloxone and, if not, what happened to any naloxone that was given to them.

Secondary Data Sources

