*Past 3 months timeline for 3 and 6 month follow ups, past 6 months used at 12 month follow up.

Brief Behavioral Change Counseling (BBCC)

The BBCC will be conducted according to the demeanor and guidelines of Motivational Interviewing (MI), a style for counseling patients about sensitive behaviors and for giving them information to enhance their health and safety in a non-judgmental manner. MI has been widely implemented in brief intervention studies for drug use and other behavior change. MI is non-confrontational and respectful of subjects' autonomy to discuss or not discuss sensitive topics. The BBCC will consist of 4 elements:

- 1) The interventionist will show to the patient an approximately 8-minute video on overdose prevention, recognition and intervention, which subjects will view on a laptop while they are using headphones. The interventionist will debrief the video with subjects and answer questions.
- 2) Next, the interventionist will review with subjects their overdose risk. This task involves informing subjects of the “good news” about overdose risks they are NOT incurring in their current behaviors for the purpose of reinforcing and hopefully continuing more positive health behaviors (e.g., not inappropriately mixing other drugs or alcohol with

opiates). Next, the interventionist will respectfully and in a neutral tone review with subjects the behaviors that currently place them at risk for opiate overdose (e.g., using opiates when alone or after a long period of abstinence).

- 3) From the video and risk feedback, the interventionist will segue into an open discussion of any changes subjects are thinking of making to increase their safety from overdosing. If at any time during the interview, subjects indicate that they would prefer to quit opiates or to seek opiate detox or treatment, the interventionist will help with these referrals. The discussion will culminate in a summary of healthy changes, if any, that subjects intend to make. Subjects will take with them a handout that has been customized to summarize any changes subjects indicate that they want to make.

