Aim 1 Test whether the intervention group has lower rates of opioid overdose and longer time to occurrence of overdose. Overdose will be ascertained at 12 months via self-report and across at least 24 months via administrative data. Because randomized controlled studies are designed to account for potential confounding factors by distributing confounders, measured and unmeasured, equally across comparison and intervention groups, the initial unadjusted analysis will be a logistic regression analysis comparing the probability of opioid overdose in the two study arms. To examine differences in the time to overdose and to account for time varying covariates, such as overdose risk factors, survival analyses will be conducted with the outcome time to overdose(s). A Cox proportional hazards model will be used to investigate the possible association between these factors and event time. We will use sandwich standard error estimates in all statistical tests. Multivariable logistic regression analyses will be conducted to examine the association between predictors and moderators and of the odds of overdose occurrence. Predictors will include treatment assignment and overdose risk factors such as concomitant drug use, interruption in tolerance and homelessness. Potential effect modification will be assessed by including interaction terms for the treatment assignment by severity of opioid and other substance use as measured by the ASSIST. For the pharmaceutical opioid only group, effect modification by opioid user type will be assessed; opioid user typologies will be based upon which inclusion criteria subjects met.

Aim 2 Test whether the intervention group has fewer overdose risk behaviors. These are measured as both binary and continuous data. Binary data will be examined with logistic

regression and continuous data analyzed with ordinary least-squares regression. Analyses will adjust for the overdose risk behavior level or frequency reported at baseline as a concomitant variable, the outcome is the overdose risk behavior at 12 months, and the primary predictor is the treatment group assignment. We will compute robust standard error estimates for each model and use them in all hypothesis tests and confidence intervals.

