In order to determine whether there is recruitment reactivity, whether those enrolled in either arm of the study have a change in behaviors compared to those not enrolled, we will examine ED re-visit rates at two years for those receiving standard care compared to those with similar demographic characteristics, CPT codes and ED visit dates, but were not enrolled. While this will not directly measure the impact of recruitment on overdose, it will provide some information about recruitment reactivity. Subsequent to intent to treat analyses we will examine whether any subjects in the standard care group received take-home naloxone and overdose prevention and intervention training i.e. “crossed over”. If so, it is possible that this intermediate group might be more similar to the intervention than the standard care group. Crossovers will be identified by an interview question, such as “Did you possess or have ready access to naloxone during the past 3/6 months?” If there is a group that crossed over, post-hoc analyses will compare overdose rates at two years for the cross over group compared to each of the other two study arms. Completion level of administrative data will be assessed by the interview questions at each follow up that document what types of services, in broad categories, were

obtained at non-HMC or non-UWMC facilities or ambulance services not in Seattle-King County. This will allow for an evaluation of *ascertainment bias*, that is, how complete data based on HMC/UWMC and King County ambulance data are and whether there are differential levels of data completion by study arm assignment.

Missing data and dropouts

Missing data will be minimized by the study procedures described above. However, missing data are inevitable and could lead to biased results. Baseline data values and study arm assignment will be examined to determine the relationship with missingness. Sensitivity analyses will be conducted that assume any person lost to follow up had constant levels of drug use based upon their most recent measurement point. This will provide some guidance as to the amount of bias possibly introduced by missing data.

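### The primary Aim 2 model uses only the 12-month value; answers at 3 and 6 months from subjects without a 12-month interview return only in a drug-use carry-forward sensitivity analysis

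*Combined protocol and SAP*

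**What the plan says.** Study Design lists "self-reported drug use and other overdose risk behaviors" among the primary outcomes, and Objectives places them under the primary aims.

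On timing, Follow-up Visits says "Follow-up visits will occur at 3, 6 and 12-month after enrollment" and "Most assessments given at the baseline interview will be repeated at each follow-up". The footnote to the data schedule gives the recall periods: "Past 3 months timeline for 3 and 6 month follow ups, past 6 months used at 12 month follow up". The schedule table itself is broken in the text available, so the visit pattern here is taken from those two places.

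For the analysis, Planned analyses (Aim 2) uses logistic regression for binary behaviours, with "regression and continuous data analyzed with ordinary least-squares regression". It adds that "Analyses will adjust for the overdose risk behavior level or frequency reported at baseline as a concomitant variable" and that "the outcome is the overdose risk behavior at 12 months". Standard errors are robust. Planned methodology makes intent to treat the main approach, but gives no rule for a subject with no outcome value.

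Missing data and dropouts accepts that some data will be missing and that this could bias results. It plans to relate missingness to baseline values and arm, and to run sensitivity analyses that "assume any person lost to follow up had constant levels of drug use based upon their most recent measurement point".

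**The concern.** The Aim 2 model has one outcome per subject, the 12-month value. As written, a subject who answered at 3 and 6 months but missed the 12-month call has no outcome and falls out of the primary analysis. Nothing in the model can use the two earlier answers. The documents do not state that the analysis is restricted to completers; it follows from the model.

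Two things are at stake: some precision, and protection against bias when interim behaviour drives who is lost. The second deserves attention in this trial. Interviews are by phone, one source of locator information is enough to enrol, many subjects are expected to be indigent, and nobody is contacted while incarcerated. Loss by 12 months could well be related to how drug use was going at 3 or 6 months. Yet the plan relates missingness only to baseline values and arm.

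**Working it through.** **1. The plan's own figure.** There is no sample size figure for Aim 2. The Aim 1 figure of 219 per arm matters here only for the loss it leaves room for. For 20% versus 10%, two-sided 0.05 and power 0.80:

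- Uncorrected: n = [1.96·√(2·0.15·0.85) + 0.8416·√(0.16 + 0.09)]² / 0.10² = 198.96, so 199.
- Continuity-corrected: (198.96/4)·[1 + √(1 + 4/(198.96·0.10))]² = 218.5, so 219. This matches.
- With 250 enrolled per arm, the implied room for loss is 1 − 219/250 = 12.4%.

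**2. Assumptions for Aim 2.** None of these is in the documents.

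- Loss at 12 months: m = 12.4%, 20% or 30%.
- Correlation between any two visits (exchangeable) or between adjacent visits (decaying, visits treated as equally spaced steps): 0.3, 0.5 or 0.7.
- Subjects missing month 12 either all have months 3 and 6, or split 40% both, 30% month 3 only, 30% neither.

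**3. Variance of the 12-month contrast.** The comparison is a likelihood-based repeated-measures model against baseline-adjusted regression on completers. If everyone missing month 12 has both earlier visits, then

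variance ratio = 1 − m·R²,

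where R² is the squared multiple correlation of month 12 with months 3 and 6, given baseline.

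- Exchangeable r: the visit-to-visit correlation given baseline is p = r/(1 + r), and R² = 2p²/(1 + p). For r = 0.5, p = 1/3 and R² = 1/6. With m = 0.20 the ratio is 1 − 0.20/6 = 0.967.
- Decaying 0.7: only month 6 adds information. The partial correlation is (0.7 − 0.7⁵)/√[(1 − 0.7⁶)(1 − 0.7⁴)] = 0.650, so R² = 0.422. With m = 0.30 the ratio is 0.873, the largest gain in the grid.
- Smallest gain: m = 12.4%, decaying 0.3, split pattern, ratio 0.995.

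| 12-month loss | Completers per arm | Effective n per arm with interim values |
|---|---|---|
| 12.4% | 219 | 220 to 231 |
| 20% | 200 | 201 to 218 |
| 30% | 175 | 177 to 200 |

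An analysis with 80.0% power on completers would have power Φ(2.802/√ratio − 1.96). Over the grid this runs from 80.2% to 85.0%.

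**4. Bias.** The illustration has no true effect, exchangeable correlation 0.5, and 20% to 30% loss in each arm. In the control arm the chance of loss rises with the 6-month value (log-odds up by 1 per SD); in the intervention arm loss is at random. Bias is intervention minus control, with higher values meaning more risk behaviour.

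| Analysis | Mechanism in control arm only | Same mechanism in both arms |
|---|---|---|
| 12-month completers | +0.04 to +0.06 SD | about 0 |
| Last value carried forward | −0.07 to −0.09 SD | about 0 |
| Model using months 3 and 6 | about 0 | about 0 |

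The sizes depend on the assumed strength of dropout and on the correlation pattern, so they are an illustration and not a bound. In the first column, carry-forward errs in the opposite direction from the completer analysis and by more.

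**The case against.** The strongest case for the plan is that one prespecified 12-month endpoint, adjusted for baseline and with robust standard errors, is a legitimate primary analysis. That stands, and the fix keeps the endpoint. The trial was powered on Aim 1, so a few percent of variance breaks no power claim for Aim 2. That stands too.

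Four stronger readings are tempting, and the documents or the arithmetic do not support them.

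- *The plan throws away everyone without a 12-month interview, and all they reported.* This is true of the primary model but not of the plan. The carry-forward sensitivity analysis brings back those subjects and their last answers, and risk factors may enter the Aim 1 survival model as time-varying covariates. The remedy is partial: it is not primary, it fills in a single value under a constant-level assumption, and it names drug use but not behaviours such as using alone or after an interruption.
- *The completer contrast is biased unless missingness depends only on arm and baseline.* This is too strong. In the illustration, dropout driven by the 6-month value left the contrast unbiased when the mechanism was the same in both arms.
- *The gain in precision is 6% to 15%.* The shortcut 1 − m·ρ², with ρ the correlation given baseline, gives 1 − 0.25·0.5² = 0.938 and 1 − 0.30·0.7² = 0.853. That needs heavy loss, earlier values for every lost subject, and a ρ that exchangeable correlation cannot reach, since r/(1 + r) stays below 0.5. At 12.4% loss and ρ = 0.5 the same shortcut gives 1 − 0.124·0.25 = 0.969, a gain of about 3%.
- *A repeated-measures model removes both problems.* It recovers only part of the lost precision, and it removes the bias only if data are missing at random given the interim values.

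**Conclusion.** The concern holds in a limited form. The primary Aim 2 analysis makes no use of months 3 and 6 and, as written, can include only subjects with a 12-month value. The only planned use of interim answers for subjects without one is a carry-forward sensitivity analysis limited to drug use. The gain in precision from using those answers is small to modest: 0.5% to 13% of the variance, or 0.2 to 5.0 power points, under the assumed loss and correlations.

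The stronger reason to act is bias when dropout depends on interim behaviour differently by arm. There the planned carry-forward check can mislead as well. Whether such dropout will occur cannot be told from the documents. This is a cheap improvement, not a flaw that invalidates Aim 2.

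**What to change.** Keep the 12-month contrast as the Aim 2 estimand and state a primary missing-data method that uses months 3 and 6.

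- **Continuous behaviours:** fit a repeated-measures model with visit, arm-by-visit and baseline-by-visit terms and unstructured covariance, and test the arm contrast at 12 months. Multiple imputation with months 3 and 6 is an alternative.
- **Binary behaviours:** impute by arm with months 3 and 6, then run the planned baseline-adjusted logistic regression with robust standard errors. A mixed logistic model is not a substitute, because it estimates a subject-specific odds ratio. With an assumed random-intercept SD of 2 and mean logit 0, a subject-specific odds ratio of 0.50 corresponds to about 0.66 on the marginal scale.
- **Recall windows:** give each visit its own mean, or analyse rates per unit time, because the window is 3 months at months 3 and 6 and 6 months at month 12.
- **Sensitivity analyses:** extend them to all Aim 2 behaviours, not only drug use.

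The cost is SAP wording and modest extra analysis work, with no new data. The drawback is reliance on a missing-at-random assumption given the interim values, which the SAP should state.

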Secondary data on health care and drug treatment utilization will be obtained from Washington State (separate IRB action pending) using the following sources:

- Treatment and Assessment Report Generation Tool (*TARGET*) for drug treatment admissions data
- The Comprehensive Hospital Abstract Reporting System (CHARS) for hospital admissions

Information on any ambulance transports will be obtained from the Seattle Fire Department's Medic 1 unit.

In the event of a subject death during the study we will request information on cause of death from the King County Medical Examiner's Office. If a subject cannot be located we will also check this source to see if they have died and if so to obtain data on the cause of death. If we are unable to locate a subject during the course of the study or at final follow-up we will utilize the King County Jail Inmate Look-up Service. At no time will subjects be contacted or study procedures attempted while the subject is incarcerated.

Intervention Description

Standard care for patients who have used opioids would vary according to individual clinical need and might include referral to drug treatment or detoxification services. Standard care would not include OOPEN and BBCC interventions as specified in this grant. After baseline data are obtained subjects assigned to the intervention undergo the following procedures:

A brief behavior change counseling (BBCC) session

- Conveys subjects' risk for overdose, based on the baseline measures
- Engages them in a reflective discussion of the pros and cons of their current patterns of use
- Has the patients identify behavior change(s) they are interested in making to improve their health
- Encourages them to share opioid overdose prevention and intervention information and materials with their family, friends, housemates, and/or drug using partners.

Education and training on opioid overdose prevention and intervention with naloxone (OOPEN)

- Subjects will view a training video on study laptops that reviews:
 - Information on risk factors for overdose and how to prevent and reduce the risk of overdose

- How to recognize an opioid overdose
- The importance of calling 911
- How to intervene in an overdose
 - Positioning a victim in rescue position
 - Brief overview of rescue breathing
 - Training on how and when to administer naloxone

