- Subjects will be given a study brochure that covers the information in the video and reviews the Washington State 911 Good Samaritan overdose law which provides immunity from prosecution for drug possession charges to overdose victims and bystanders who seek aid in an overdose event.
- Prescribing and dispensing overdose rescue kits including 2 doses of intra-nasal naloxone, a disposable rescue breathing mask, and disposable gloves.
- Subjects in the intervention group will be informed that they may have one replacement of the naloxone kit (2 doses) during the 12 month study period.

We expect the intervention to take 30-45 minutes on average based on our experience and that this is feasible and reasonable for subjects and interventionists.

Fidelity assessment for the BBCC will be done with the shortened Motivational Interviewing Treatment Integrity (MITI) instrument.

Schedule of and Sources Data Obtainment

MEASURES	DATA SOURCES AND TIMING					
	Interview			Administrative		
	Case Report Form	Base-line	3 & 6 mos.	12 mo.	Up to 10 yrs.	Up to 10 yrs.
PRIMARY AIMS						
Aim 1: Overdose						
Subject overdosed prior 3/6* months	X		X			
Subject overdosed Y/N & Date						X
Aim 2: Drug use and other overdose risk behaviors						
Alcohol/Drugs 3/6 month use frequency	X		X		X	
Opioid use following interruption past 3/6 months	X		X		X	
Using opioids without others present	X		X		X	
Avg. daily opioid dose- Prescribed Opioid Users	X		X		X	
Opioid substitution drug treatment prior 3/6	X		X		X	
Other drug treatment sought or used prior 3/6	X		X		X	
SECONDARY AIMS						
Aim 3: Health care utilization						

ED, Outpatient, Inpatient and Ambulance- # & Aim 4: Health care costs Hospital-based total direct health care costs			x	x
Aim 5: HIV Risk Behaviors	x	x	x	x
CO-VARIATES & POTENTIAL EFFECT MODIFIERS				
Demographics	x			
Employment, health insurance, income, housing	x	x	x	
Alcohol/Drugs ages of first use	x			
Medical status and satisfaction (WHO QOL BREF, EQ-5D- 3L)	x	x	x	
Behavior change plans and readiness	x			
Overdose lifetime history	x			
Possessed, "carried" naloxone, # of days past 3/6	x	x	x	
Overdose # witnessed events past 3/6 months	x	x	x	
Source of naloxone- Study, other	x	x	x	
Subject had naloxone administered to them, #, by Disposition of naloxone	x	x	x	x
Subject had negative/allergic reaction to naloxone	x	x	x	
FIDELITY ASSESSMENT OF BASELINE				
Overdose prevention & intervention training. Item Motivational Interviewing Treatment Integrity 3.1.1	x			

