Aims 3 and 4 Test whether the intervention group has more appropriate health care utilization and lower total health care costs. We will analyze utilization for three separate outcomes: ED visits, outpatient visits, and inpatient hospital admissions as we would expect the intervention to result in declines in ED and inpatient care with concomitant increases in outpatient care over time as patients stabilize their health status. For these analyses we will use a rate modeling approach (negative binomial or Poisson regression, with an exposure adjustment should there be a need to account for differing amounts of follow-up time). We will examine health care costs (combined hospital and ambulance costs) from the health care system perspective.

Mean-per-month health care costs will be calculated for both pre- and post-randomization periods for each individual. We will assess the difference in health care costs across the two study arms by regressing post-randomization mean health care costs on study arm, and controlling for pre-randomization mean health care costs (which should reduce variance and increase power) along with other important covariates. We expect that 500 per arm will be an adequate number to support the use of Ordinary Least-Squares (OLS) regression to model mean cost differences, but will use Generalized Linear Models (GLM) models to examine the sensitivity of OLS results. In addition, we will calculate unadjusted and adjusted cost offsets by adding the cost of the intervention to health care costs and comparing average monthly total costs of services for the intervention group to the average for the standard care group.

Aim 5 Test whether the intervention group has fewer HIV risk behaviors. These are measured as both binary and continuous data. Binary data will be examined with logistic regression and continuous data analyzed with ordinary least-squares regression.

Other analyses

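### Aim 3 counts ED and outpatient visits from records that appear to cover only HMC/UWMC, and the planned completeness check can flag care obtained elsewhere but cannot quantify or correct for it

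*Combined protocol and SAP*

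**What the plan says.** Under Planned analyses, Aims 3 and 4, the plan says: "We will analyze utilization for three separate outcomes: ED visits, outpatient visits, and inpatient hospital admissions". It expects "declines in ED and inpatient care with concomitant increases in outpatient care over time as patients stabilize their health status". The model is "negative binomial or Poisson regression, with an exposure adjustment should there be a need to account for differing amounts of follow-up time". Follow-up time is the only adjustment named in that sentence; incomplete capture of visits is not mentioned. The data schedule has an Aim 3 row headed "ED, Outpatient, Inpatient and Ambulance", marked as a number.

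Secondary Data Sources lists two state files: TARGET for drug treatment admissions, and "The Comprehensive Hospital Abstract Reporting System (CHARS) for hospital admissions". Ambulance transports come from the Seattle Fire Department's Medic 1 unit.

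Other analyses plans a completeness check. Questions at each follow-up interview will "document what types of services, in broad categories, were" obtained at facilities other than HMC or UWMC. The answers are to show "how complete data based on HMC/UWMC and King County ambulance data are", and whether completeness differs by arm. Interviews take place at 3, 6 and 12 months; administrative follow-up runs for at least 24 months (Study Design).

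The sites are HMC, "University of Washington Medical Center (UWMC), and Evergreen Treatment Services". The section on the oversight committee describes Evergreen as a methadone maintenance clinic. The residence criterion is Washington State.

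**The concern.** Aim 3 is a hypothesis about substitution: less emergency and inpatient care, more outpatient care. Testing it requires counts of each type of visit. Admissions have a state source. For ED visits without admission and for outpatient visits, the only facility data indicated are those of two hospitals. Subjects may live anywhere in the state, and one of the three sites is a clinic whose patients need not use either hospital.

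The plan does not say where the added outpatient care would be delivered. If much of it is at community clinics, those visits do not enter the count, and the intervention's predicted benefit on this outcome is diluted. The interview item cannot restore it. A subject with one outside clinic visit and a subject with ten give the same answer to a question about type of service, and nothing is asked after month 12. The plan also states no consequence for the Aim 3 models if completeness proves to differ by arm.

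**Working it through.** **Plan's own figure.** The plan gives no visit rate, effect size, capture share or power for Aim 3, so there is nothing to reproduce. Its 219 per arm belongs to Aim 1 (20% against 10%, power 0.80). A two-sided 0.05 test with continuity correction returns 219, but this point does not depend on it.

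**Step 1: trace each outcome to its source.**

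| Aim 3 outcome | Source in Secondary Data Sources | Reach indicated |
|---|---|---|
| ED visits | none named | HMC/UWMC (Other analyses) |
| Outpatient visits | none named | HMC/UWMC (Other analyses) |
| Inpatient admissions | CHARS | state file of hospital admissions |

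TARGET may show entry into drug treatment, but as admissions, not as outpatient visits.

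**Step 2: effect on the rate ratio.** Inputs, all assumed:
- R = 1.25, the true outpatient rate ratio
- c, the share of usual visits that is captured
- e, the share of the intervention's added visits that is captured

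With the control rate set to 1:

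observed ratio = [c + e(R − 1)] / c = 1 + (e/c)(R − 1)

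- e = c: 1 + 1 × 0.25 = 1.25
- e = c/2: 1 + 0.5 × 0.25 = 1.125
- e = c/4: 1 + 0.25 × 0.25 = 1.0625
- e = 0: 1 + 0 = 1.00

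Only e/c matters. Low capture alone does not bias the ratio; capturing added visits less well than usual visits does.

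**Step 3: the same result as capture by arm.** Overall capture in the intervention arm is [c + e(R − 1)] / R. Take c = 0.60 (assumed):
- e = 0.30: (0.60 + 0.30 × 0.25) / 1.25 = 0.675 / 1.25 = 0.54, and 1.25 × 0.54 / 0.60 = 1.125
- e = 0: 0.60 / 1.25 = 0.48, and 1.25 × 0.48 / 0.60 = 1.00

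So under these inputs a difference of 60% against 54% in captured visits halves the excess. A type-of-service item cannot measure that share, because it does not count visits.

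**Step 4: illustrative power.** Further assumptions: control mean of 8 outpatient visits over two years, so 8 × 0.60 = 4.8 recorded, and negative binomial dispersion k.

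SE = √[(1/μ0 + k)/n + (1/μ1 + k)/n], power = Φ(ln(observed ratio)/SE − 1.96)

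For n = 500 and k = 1 with e = c/2: μ1 = 4.8 × 1.125 = 5.4, SE = 0.0692, ln 1.125 = 0.1178, and 0.1178/0.0692 = 1.70, giving 0.398.

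| n per arm, k | e = c | e = c/2 | e = c/4 |
|---|---|---|---|
| 500, 1 | 0.899 | 0.398 | 0.139 |
| 500, 2 | 0.665 | 0.241 | 0.094 |
| 250, 1 | 0.629 | 0.225 | 0.090 |

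Both sizes are shown because the Aim 3 text does not say whether user types are pooled (250 per arm in each type, 500 combined). With every visit captured, 500 per arm and k = 1, power is 0.917. Equal 60% capture therefore costs almost nothing (0.917 to 0.899); the loss comes from where the added visits go.

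**The case against.** The strongest reply is that the sponsor has seen the problem. Other analyses plans to assess completeness and compare it by arm, and a difference between arms is what would bias a randomized comparison. Two of the three sites are the hospitals that hold the records, and screening covers proximity to the research settings. Records-based counts do not depend on reaching subjects by phone, whereas self-reported counts bring recall error and missed interviews. Aim 3 is also secondary, and the sample size was set for Aim 1.

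Most of this stands, and it limits the point. The check deserves credit as a warning signal, and the records should stay the basis of the main analysis. What the reply does not answer is that an item recorded by type, ending at month 12, gives no size for the missing care.

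Three stronger readings are tempting, and the documents do not support them:
- **Every visit elsewhere is certainly lost.** The HMC/UWMC limit is an inference from the source list and from Other analyses. Subjects also authorize release of medical and drug treatment records from secondary sources, although no further one is named. The Aim 3 row of the data schedule is broken in the extracted text, so it cannot settle whether interviews also collect counts.
- **An apparent fall in ED visits would be an artefact of subjects switching hospitals.** Switching biases the comparison only if it differs by arm, and the documents give no mechanism for that. The Background also says that nearly all medic-attended opioid overdoses in Seattle go to the HMC ED.
- **The outpatient shift cannot be seen at all.** A recorded ratio of 1.00 requires that none of the added visits be captured, which is one end of the range.

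**Conclusion.** The point holds in a limited form. As written, the plan models ED and outpatient visit rates with no named source that counts them beyond HMC/UWMC, and its completeness check can flag differential capture but cannot quantify or correct it. Equal capture across arms and visits does no harm to the rate ratio. If added outpatient care goes disproportionately elsewhere, the predicted increase is attenuated and can go unseen: an assumed true 1.25 appears as anything from 1.25 down to 1.00, and as 1.125 when added visits are captured half as well as usual ones. The ratios rest on the assumed 1.25 and on e/c; the power figures rest also on the assumed visit rate, 60% capture and dispersion. None of these inputs is in the documents. The conclusion would change if the sponsor names a further source or confirms that interviews already collect counts.

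**What to change.** 1. At 3, 6 and 12 months, make the existing outside-care item numeric: the number of ED visits, outpatient visits and admissions at facilities other than HMC and UWMC. The schedule's recall windows (past 3, 3 and 6 months) add up to 12 months, so the counts can be summed.
2. Keep the records-based rate model as the main Aim 3 analysis. Add a 12-month sensitivity analysis of recorded plus reported outside ED and outpatient visits, and report by arm the share of visits captured in records.
3. Describe the records-only ED and outpatient results as HMC/UWMC utilization, not total utilization, unless a further source is named.

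The cost is one reworded item, one added analysis and a change of label. The downsides are recall error, dependence on completed interviews in a population that may be enrolled with a single locator source, and possible arm-related reporting because subjects know their arm. These are the reasons to use the reported counts as a sensitivity analysis and not as the main one. The item still gives nothing beyond month 12, so the label in item 3 matters most for the 24-month results.
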